4.3 Study Schedule

Table 1: Study procedures (from study protocol)

Study procedures				
Study procedures	Baseline Visit Day 0	Week 4 ^a	Week 8 ^b	Follow-up Visit Week 12 or early termination ^b
Informed Consent	X			
Inclusion/Exclusion Criteria	X			
Urine Pregnancy Test	X		X	
Randomization	X			
Demographics	X			
Ocular and General Medical History	X			
Previous and Concomitant Ocular And Systemic Medications	X	X	X	X
Frequency of Artificial Tear Use	X			X
Record Adverse Events (AEs)	X	X	X	X
Verify Patient Study Medication Dosing Compliance		X	X	
SANDE ^c questionnaire	X	X	X	X
Best Corrected Distance Visual Acuity (BCDVA)	X	X	X	X
Schirmer test I (without anesthesia)	X		X	
External Ocular Examination	X	X	X	X
Slit-lamp Examination (SLE)	X	X	X	X
Fluorescein and lissamine green staining (NEI scale)	X	X	X	X
Tear Film Break-up Time (TFBUT)	X	X	X	X
InflammaDry (MMP-9)	X		X	
Study Drug Dispensation	X	X		

a) Visit window of ± 2 days; b.) Visit window of ± 4 days; c.) SANDE - Symptom Assessment In Dry Eye

4.4 Efficacy and Safety Variables

In the study protocol the following study endpoints are specified.

Primary endpoint

- *Change from baseline in SANDE scores for severity and frequency assessed at 8 weeks of treatment (with LOCF imputation at earlier end of trial assessment)*

Secondary endpoints

- *Change from baseline in SANDE scores for severity and frequency assessed at 4 and 8 weeks of treatment (without using LOCF)*
- *Changes in Cornea and conjunctival vital staining with fluorescein, National Eye Institute (NEI) scales*
- *Changes in Tear film break-up time (TFBUT) and Schirmer test I*

Exploratory endpoint

- *Changes in Levels of the inflammatory biomarker matrix metalloproteinase 9 (MMP-9) in tears, measured by the RPS Inflamm Dry detector*

Safety endpoint

- *Incidence and frequency of Treatment-emergent adverse events (TEAEs), assessed throughout the study*

4.5 Interim Analyses

No interim analyses are planned.

4.6 Sample Size estimation

Sample size was calculated by assuming both for severity and frequency a mean difference from baseline SANDE score of -30 ± 20 in the rhNGF groups versus -20 ± 20 in vehicle group (80% power, $\alpha = 0.05$; 2-sided t-test), considering that the active comparator has already proven safe and effective in dry eye patients.

Testing hypotheses are:

H0: mean change from baseline rhNGF = mean change from baseline Vehicle = 0

H1: mean change from baseline rhNGF = mean change from baseline Vehicle = -10

Therefore, the sample size has been calculated based on a 2:1 randomization scheme for inference with Student t test for independent groups using PS Power and Sample Size Calculations (<http://biostat.mc.vanderbilt.edu/PowerSampleSize> Version 3.0, January 2009 Copyright © 1997-2009 by William).

If the true difference in the experimental and control means is 10 (estimated from our internal study), we will need to study 96 experimental subjects and 48 control subjects to be able to reject the null hypothesis that the population means of the experimental and control groups are equal with probability (power) 0.8 and with standard deviation of 20. The Type I error probability associated with this test of this null hypothesis is 0.05.

Considering a 5% drop out, 150 patients will be included in the study: 100 patients in rhNGF group and 50 patients in vehicle group.

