10.2 Sample size and power considerations

Sample size was calculated by assuming both for severity and frequency a mean difference from baseline SANDE score of -30 ± 20 in the rhNGF groups versus -20 ± 20 in vehicle group (80% power, $\alpha = 0.05$; 2-sided t-test), considering that the active comparator has already proven safe and effective in dry eye patients. Therefore, the sample size has been calculated based on a 2:1 randomization scheme by the following formula:

$$n_1 = (0.5) \times n \times (1 + k)$$

$$n_2 = (0.5) \times n \times (1 + (1/k))$$

With n_1 = active treatment, n_2 = vehicle, $n = 63$, and $k = n_1/n_2 = 2/1=2$. Therefore, $n_1 = 94.5$ and $n_2 = 47.25$. Assuming a 5% dropout rate, a total of 100 patients will be enrolled in the active arm, and 50 in the vehicle arm.

Since this is an exploratory study, no adjustment has been made for multiplicity of SANDE parameters, neither has it been taken into account that the actual analysis will be descriptive only.

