4.7 Changes in the Conduct of Study or Planned Analysis compared to protocol/CIP

This SAP implements the subsequent deviations from the analysis specification of the study protocol:

- An updated sample size estimation is given in the SAP to provide a more detailed explanation about the underlying statistical assumptions of the study.
- The RPS InflammDry does not provide specific MMP-9 levels, but is only providing a qualitative assessment “Positive” or “Negative”. As a consequence, the exploratory endpoint “changes in Levels of MMP-9” could not be evaluated. This evaluation will be replaced by providing a shift table displaying qualitative test results of Week 8 vs. Baseline.
- Definition of Screen Failures. In the study protocol (section 10.1.1) a screen failure is defined as patient who is not eligible, i.e. is not respecting all the inclusion/exclusion criteria. According to the study protocol, such patients should not be randomized and enrolled.
To streamline presentation of patient flow for reporting and to extend definition also for protocol deviations, screen failure will be defined as screened patients, who are not randomized. By this, patients, who were randomized although they did not comply with eligibility criteria will not be considered as screen failure. On the contrary, patients, who comply with all eligibility criteria but dropped out from the study before randomization (e.g. due to consent withdrawal) will be considered as screen failure.
- Definition of Safety Set: The protocol defines the Safety Set as all enrolled patients who receive at least one dose of study medication at the study eye. This is adapted to all enrolled patients, who receive at least one dose of study medication irrespective of administered eye, as also study medication given in the non-study eye are also under risk of developing undesired side effects and should therefore be part of safety evaluation.
- Definition of compliance: in section 10.3, the study protocol demands further compliance definitions based on diary card information to investigate compliance with study eye treatment. However, as no eye-specific assessments were recorded on diary card, no such definitions were established.

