- In the study protocol, no inferential analyses are specified. However, purely exploratory 95% confidence intervals and hypothesis testing for the difference between treatment groups will be implemented in the SAP on sponsor’s request. These inferential procedures will be purely exploratory without adjusting for type I error rate.
- Note to File (“NGF0216 Sande Questionnaire Endpoints”, dated 25SEP2017) clarified the administration instructions of the SANDE questionnaire.

5 General Definitions

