8.2.7 Efficacy Variables

Primary and Secondary Endpoints: Sande Score

The Symptom Assessment in Dry Eye (SANDE) questionnaire is a short questionnaire to evaluate both dry eye intensity and frequency by using a 100 mm visual analogue scale (VAS). The patient symptoms of ocular dryness and/or irritation will be quantified on the scale based on two questions that assess both severity and frequency of symptoms.

For the assessment, the patients mark on the 100 mm VAS line the point that they feel represents their perception of their current state. The VAS score is determined by measuring in millimeters from the left hand end of the line to the point that the patient marks. The SANDE scores will be then evaluated for the 2 questions severity (0-100) and frequency (0-100).

The Note to File (“NGF0216 Sande Questionnaire Endpoints”, dated 25SEP2017) clarifies the administration instructions of the SANDE questionnaire.

The Sande score will be assessed at Baseline, Week 4, Week 8 and Week 12 visit and is recorded on the eCRF page ‘Symptoms Assessment in Dry Eye’. At each visit, only one assessment is performed aggregating the situation for both eyes (i.e. no separate assessment per study eye).

Primary endpoint will be defined as:

- Change from Baseline in Sande frequency score at Week 8
- Change from Baseline in Sande severity score at Week 8,
i.e. Week 8 score recorded on the eCRF minus the Baseline score on the eCRF

If at least one Sande assessment is missing at Week 8, the values of the last post-baseline assessment (including those from unscheduled visits) with non-missing values for frequency and severity will be imputed (LOCF). No imputation is performed in case of a missing baseline value (as defined in section 8.1).

Additionally, Sande frequency and severity scores as well as respective changes from Baseline will be evaluated without any imputation for Week 4, Week 8 and Week 12, respectively.

Secondary Endpoints: Ocular Surface Staining (NEI Scale)

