9.2 Specific Methods for Efficacy Analyses

As a general principle, all secondary efficacy analyses will be performed for the study eye only. Efficacy data in non-study eye will be listed.

For the primary and secondary endpoints, mean change from baseline will be compared between treatment groups for the study eye. The null hypothesis will be tested that there is no difference between rhNGF and vehicle in the mean overall change from baseline between both treatments:

$$H_0: \mu_{\text{rhNGF}} = \mu_{\text{Vehicle}}$$

$$H_1: \mu_{\text{rhNGF}} \neq \mu_{\text{Vehicle}}$$

Where μ is the mean change from baseline at considered visit within the given treatment.

This hypothesis will be tested exploratory at a 5% level of significance with an Analysis of the Covariance (ANCOVA) with treatment and respective baseline value in the model. The Least-squares means estimate of the treatment effect and the treatment group difference (both with 95% confidence intervals) will be reported. P-values will be rounded to three decimal places. If a p-value is less than 0.001 it will be reported as "<0.001". Due to the high numbers of observations, the assumption of normality is assumed.

The analysis will be performed for the following endpoints:

- Change from Baseline in Sande Frequency and Severity Score at Week 8 (LOCF) for the FAS as exploratory primary efficacy analyses
- Change from Baseline in Sande Frequency and Severity Score at Week 8 (LOCF) for the PPS as supportive to primary efficacy analyses

- Change from Baseline in Sande Frequency and Severity Score (without imputation) at Week 4, Week 8 and Week 12 for the FAS as supportive to primary efficacy analyses
- Change from Baseline in Corneal and Conjunctival staining at Week 4, Week 8 and Week 12 for the FAS as well as PPS as exploratory secondary efficacy analyses
- Change from Baseline in TFBUT at Week 4, Week 8 and Week 12 for the FAS as well as PPS as exploratory secondary efficacy analyses
- Change from Baseline in Wetting Distance (5 minutes) at Week 8 for the FAS as well as PPS as exploratory secondary efficacy analyses.

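### Do the hypotheses printed in SAP 4.6, which set the two arms equal under both H0 and H1, undermine the SANDE tests or the sample size?

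*SAP*

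**What the plan says.** SAP 4.6 gives one pair of testing hypotheses, "H0: mean change from baseline rhNGF = mean change from baseline Vehicle = 0" and "H1: mean change from baseline rhNGF = mean change from baseline Vehicle = -10". Before the pair, it states the assumptions for both SANDE items: mean change -30 for rhNGF and -20 for vehicle, SD 20 in each arm, 80% power, two-sided 5%. After it, the section names Student's t test for independent groups and continues: "If the true difference in the experimental and control means is 10", 96 and 48 patients give power 0.8 to reject equality of the two population means. The 0.05 is attached to that null.

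SAP 4.7 introduces the section with "An updated sample size estimation is given in the SAP to provide a more detailed explanation".

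SAP 8.2.7 defines the primary endpoint as two changes: "Change from Baseline in Sande frequency score at Week 8", and the same for severity. SAP 9.2 tests equal against unequal mean changes by ANCOVA with treatment and baseline: "This hypothesis will be tested exploratory at a 5% level of significance".

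On multiplicity, Protocol 10.2 says that the sizing was not adjusted for the two SANDE parameters, "neither has it been taken into account that the actual analysis will be descriptive only". SAP 4.7 then adds confidence intervals and tests: "These inferential procedures will be purely exploratory without adjusting for type I error rate". SAP 9.2.1.1 and 9.2.1.3 repeat that nothing is adjusted.

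**The concern.** Under the printed H1 both arms change by -10, so the drug does nothing. Under the printed H0 both arms change by 0, which is already false if vehicle patients improve by the assumed 20. Neither line matches SAP 9.2 or the -30 against -20 in the same section. Since SAP 4.7 says the section was rewritten to explain the assumptions, a reader could fairly ask which test the 80% belongs to.

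Two further points arise in the same place. The primary endpoint has two items, but 4.6 gives one 5% and one 80% without saying that they hold for each item separately. And no section says how a split result, one item below 0.05 and the other not, would be described. If the printed hypotheses governed the analysis, or if a claim hung on either p-value, the reading of the primary result would be at stake.

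**Working it through.** **1. The plan's own figure.** Inputs from SAP 4.6: difference 10, SD 20, two-sided 5%, power 80%, allocation 2:1.

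Normal approximation for the vehicle arm:

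n = (1 + 1/2) × [SD × (z₀.₉₇₅ + z₀.₈₀) / difference]² = 1.5 × [20 × (1.960 + 0.842) / 10]² = 47.1

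This rounds up to 48 vehicle and 96 rhNGF, the stated numbers.

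Power by the t test:
- standard error = 20 × √(1/96 + 1/48) = 3.54
- non-centrality = 10 / 3.54 = 2.83, with 142 degrees of freedom
- power from the non-central t distribution = 0.802 (normal approximation 0.807)

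Protocol 10.2 uses the same contrast. Its n = 63 for equal arms is 2 × [20 × 2.802 / 10]² = 62.8, rounded up.

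**2. What the printed lines would give.** Under the printed H1 the between-arm difference is -10 - (-10) = 0. The test in 9.2 then rejects 5.0% of the time at any sample size, so no calculation could have reached 96 and 48 from it. Reading the second equals sign as a minus gives rhNGF minus vehicle = 0 for H0 and -10 for H1. The latter equals -30 - (-20) and is the difference used in step 1.

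The printed H0 can be pushed the same way. A joint test that both arms have zero change would reject more than 99.9% of the time with both arms at -20 (N = 144, SD 20, non-centrality 144). The SAP plans no such test, so the figure says nothing about this trial.

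**3. Statements side by side.**

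| Place | Null | Alternative |
|---|---|---|
| SAP 4.6, symbols | both arms 0 | both arms -10 |
| SAP 4.6, sizing text | population means equal | true difference 10 |
| SAP 9.2 | mean changes equal | mean changes unequal |

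The symbols are the outlier. A point alternative for sizing beside a two-sided alternative for testing is ordinary practice, so the last two rows do not conflict.

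**4. Per item or overall.** SAP 4.6 makes its assumptions for severity and for frequency, and each item is tested on its own in 9.2. The 0.802 is therefore a per-item power. The correlation between items is not in the documents. For an assumed range, at 96 and 48 patients (bivariate normal):

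| Assumed correlation | At least one false positive | Power, at least one item | Power, both items | Split (any minus both) |
|---|---|---|---|---|
| 0.5 | 9.1% | 91.8% | 69.7% | 22% |
| 0.7 | 8.4% | 89.2% | 72.2% | 17% |
| 0.9 | 7.0% | 85.6% | 75.9% | 10% |

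The last three columns suppose a true difference of 10 on both items. None of these rates is hidden by the plan: both documents disclose that nothing is adjusted.

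**The case for a change.** The best case for acting is that a hypothesis statement should be right, whatever the status of the study. Exploratory status excuses the absence of alpha adjustment. It does not excuse an alternative that says the drug has no effect, in a section offered as the fuller explanation, and correcting it costs two lines before unmasking. A split result would also not be rare (10% to 22% under the assumed correlations), and a sentence written in advance would discourage leaning on whichever item succeeds.

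The first part stands as a matter of fact: the two lines are wrong as they read. A minus sign lost in converting the PDF to text cannot be excluded, though other minus signs in the section survive. What does not follow is any consequence. The sizing text ties the 80% and the 5% to the correct null, so the question of which test they belong to is answered a few lines below the error.

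The split-result point is a preference. SAP 9.2 already reports the treatment difference with a 95% confidence interval for both items, and SAP 10.5.1 places both in the primary analysis. No success rule or decision depends on either p-value. Protocol 10.2's remark that the analysis would be descriptive only is out of date, but SAP 4.7 declares that change openly.

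**Conclusion.** This is a clerical slip with no effect on the plan. The two hypothesis lines in SAP 4.6 equate the arms where they should subtract them, while the words of the same section and the operative hypotheses in SAP 9.2 are correct. The sizing of 96 and 48, the power of 0.802 per item, the two-sided 5% level, the ANCOVA and the exploratory status are the same before and after the symbol is corrected. A statistician programming from 9.2 would never use the lines in 4.6.

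The missing per-item label is a gap that any analyst fills the same way, and the absence of multiplicity adjustment is disclosed in both documents. The conclusion rests on reading the equals sign as a minus, which is the reading consistent with -30 against -20 and with the reproduced sample size. It does not depend on the between-item correlations, which are assumptions.

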4.7 Changes in the Conduct of Study or Planned Analysis compared to protocol/CIP

This SAP implements the subsequent deviations from the analysis specification of the study protocol:

- An updated sample size estimation is given in the SAP to provide a more detailed explanation about the underlying statistical assumptions of the study.
- The RPS InflammDry does not provide specific MMP-9 levels, but is only providing a qualitative assessment “Positive” or “Negative”. As a consequence, the exploratory endpoint “changes in Levels of MMP-9” could not be evaluated. This evaluation will be replaced by providing a shift table displaying qualitative test results of Week 8 vs. Baseline.
- Definition of Screen Failures. In the study protocol (section 10.1.1) a screen failure is defined as patient who is not eligible, i.e. is not respecting all the inclusion/exclusion criteria. According to the study protocol, such patients should not be randomized and enrolled.
To streamline presentation of patient flow for reporting and to extend definition also for protocol deviations, screen failure will be defined as screened patients, who are not randomized. By this, patients, who were randomized although they did not comply with eligibility criteria will not be considered as screen failure. On the contrary, patients, who comply with all eligibility criteria but dropped out from the study before randomization (e.g. due to consent withdrawal) will be considered as screen failure.
- Definition of Safety Set: The protocol defines the Safety Set as all enrolled patients who receive at least one dose of study medication at the study eye. This is adapted to all enrolled patients, who receive at least one dose of study medication irrespective of administered eye, as also study medication given in the non-study eye are also under risk of developing undesired side effects and should therefore be part of safety evaluation.
- Definition of compliance: in section 10.3, the study protocol demands further compliance definitions based on diary card information to investigate compliance with study eye treatment. However, as no eye-specific assessments were recorded on diary card, no such definitions were established.
- In the study protocol, no inferential analyses are specified. However, purely exploratory 95% confidence intervals and hypothesis testing for the difference between treatment groups will be implemented in the SAP on sponsor’s request. These inferential procedures will be purely exploratory without adjusting for type I error rate.
- Note to File (“NGF0216 Sande Questionnaire Endpoints”, dated 25SEP2017) clarified the administration instructions of the SANDE questionnaire.

5 General Definitions

5.1 Report Language

All TLFs will be prepared in English.

5.2 Analysis Software

The statistical analysis will be performed using the SAS[®] statistical software package (Statistical Analysis System, Version 9.3 or later).

6 Data Preparation

6.1 Data Handling and Medical Coding

For data quality control and medical coding please refer to the Data Management Plan including the Data Validation Plan in its most recent version.

6.2 CDISC

All output as defined in the SAP will be generated based on CDISC ADaM datasets following ADaM implementation Guide 1.0, as per contract with Dompé farmaceutici S.p.A.. SDTM programming will follow SDTM version 1.3 together with SDTM implementation guide 3.1.3.

Specifications for the ADaM datasets (as well as SDTM datasets) are described in a separate document.

6.3 SAS-Programming Quality Level

The following quality level of programming deliverables will be applied, as per contract with Dompé Farmaceutici S.p.A.. All statistical output will receive a tailored Quality Control (QC) approach by:

- Full independently double programmed reproduction (QC) of CDISC:
 - SDTM datasets
 - ADaM datasets
- Full independently double programmed reproduction (QC) of results of
 - Primary endpoint analysis and its underlying analysis dataset(s) and table(s),
 - Randomization merging
 - Analysis population merging, and
 - Visit windows programming
- Listings will not be double programmed.
- All other inferential analyses, tables, profiles and accompanying derived analysis datasets (i.e. disposition, demographics, baseline characteristics, adverse events, laboratory and vital signs) will be given a reduced QC involving independent reproduction (i.e. double programming or manual cross checking a subset of patients) of approximately 10% of the summary results (selection to be agreed upon with the sponsor).
- All tables and listings will undergo comparison with specification (i.e. SAP and templates), cross checking with other tables and listings, a sensibility review and SAS-log review.

7 Analysis Sets and Subgroups

7.1 Analysis Sets

A patient will be defined as *screened* after the signature of the informed consent, regardless of the completion of all the screening procedures. A patient will be defined as screen failure, if he was screened but not enrolled in the study.

Enrolled Set:

A patient will be defined as *enrolled* in the study if he/she is randomized. This analysis set will be used for demographic, baseline and background characteristics.

If not stated otherwise, analyses based on the Enrolled Set will be summarized by the treatment randomized.

Safety Set (SAF):

The Safety Set will be defined as all enrolled patients who receive at least one dose of the investigational medicinal product (IMP). *This analysis set will be used for the safety analysis.* All analyses based on the SAF will be summarized by the treatment received.

Full Analysis Set (FAS):

The Full analysis set will be defined as all patients in the SAF, who have receive at least one dose of the IMP in the study eye and who have at least one post-baseline Sande score assessment or another post-baseline efficacy measurement in the study eye. This analysis set will be used for efficacy analyses. All efficacy analyses based on the FAS will be summarized by the treatment randomized.

Per Protocol Set (PPS):

The Per Protocol set will be defined as *all patients in the FAS who fulfill the study protocol requirements in terms of investigational medicinal product intake and collection of primary efficacy data and with no major deviations that may affect study results. This analysis set will be used for supportive efficacy analysis.* All efficacy analysis based on the PPS will be summarized by the treatment randomized.

After all patients have completed study and prior to database lock, a blinded data review meeting (BDRM) will be performed to assign patients to analysis sets. Details of BDRM will be specified in a separate BDRM-plan.

The BDRM plan will consider the following criteria for exclusion of a patient from the PPS:

- *lack of compliance with investigational medical product administration*

A compliance below 80% or greater than 120% will lead to exclusion from the PPS (compliance definition please refer to section 8.2.5).

- *exposure to an IMP dose different from the one assigned to the patient*

- *missing primary efficacy data*
- *failure to satisfy any inclusion/exclusion criteria (eligibility violations)*
- *intake of prohibited medications*

Moreover, a review of protocol deviations and potential consequences for the analysis will be evaluated during the BDRM. The results of the BDRM will be summarized in BDRM Minutes, which will be finalized before unmasking.

